4. RESEARCH QUESTION/AIM(S)

The research question underpinning the project is as follows, “Can the use of dynamic compression shorts during daily activities improve short term treatment outcomes in hip dysplasia patients?”.

In the context of this non-blinded, non-randomised cohort feasibility study the objective is to establish potential for further comparative interventional study. The primary outcome measure will be Functional status and health-related quality of life, as evaluated by the International Hip Outcome Tool 12 (iHOT 12).

Secondary outcomes applied are:

- Hip degree of motion strength testing- force
 - measured by hand dynamometer
- Goal Attainment Scaling (GAS) questionnaire
 - evaluating the extent to which patient's individual goals are achieved over the course of study intervention in the categories sport/recreation, occupation, social, lifestyle
- Hospital Anxiety & Depression Scale
 - Effect on mental health
- OPUS HQOL STATUS (2014)
- OPUS LOWER EXTREMITY FUNCTIONAL STATUS (2014)
- OPUS SATISFACTION (2014) Qs 1-9 fit and comfort of the Orthotic garment intervention.
 - These subscales are used for prosthetic and orthotic programs for quality assessment, to maintain awareness of improvement in activities, to evaluate changes in patient's functional status and quality of life, and to assess satisfaction with devices and services.

4.1 Objectives

This study is intended to establish the experience of patients within the limited duration of the study, of prescribed exercise wearing the shorts and also daily use of the shorts in self-selected sport, leisure and activities of daily living. An important aspect of the study is to establish the importance of underlying, secondary or negative factors that may contribute to the net treatment effect. Thus, we will gather valuable information about the feasibility of using this garment, not only as part of a limited term intervention for study or treatment but their effect on an individual's quality of life and practicality as an aid for longer term use.

4.2 Outcome

This feasibility study will refine the research protocol and measures, identify any complications of garment use, establish compliance and feedback on aspects of experience; gathering early evidence of effect and establish potential for future interventional study. The intention of this study is primarily to establish the practicality of studying the effects of the garments over the period of a study and assess the justification for further quantitative study, rather than the adjunctive effect of the shorts themselves. The findings will inform the development of a study design which can more fully establish the generalisable degree to which this intervention can deliver effective relief from pain and disability for patients with hypermobility and hip dysplasia.

5. STUDY DESIGN, METHODS OF DATA COLLECTION AND DATA ANALYSIS

This prospective, 2 x repeated measures, non-blinded, non-controlled study will invite a cohort of patients to take part in a study that combines usual care with adjunctive use of DLS for a limited period of 8-12 weeks, in accord with the Declaration of Helsinki.

The null hypothesis in relation to the primary outcome measure can be stated as follows: 'use of dynamic compression shorts during daily activities does not modify the degree of pain experienced by hip dysplasia patients.'

Protocol: Patient screened by the clinical care team, will be invited to participate by the medical team, based upon the inclusion and exclusion criteria specified. They will be provided with an information sheet (PIS). The medical team will pass the prospect's details to the research team who will subsequently make contact to invite to the initial, face to face baseline session. If the patient for any or no reason declines to continue at this or any point, they will continue on the standard treatment pathway.

Recruitment session: If the patient agrees to attend, they will attend at the research site. The researcher will affirm that the prospects have read and understood the PIS information. Written consent will be sought and witnessed. Hypermobility status will be evaluated. The shorts will be measured (a single circumferential tape measure at the level of the anterior superior iliac crests (ASIS)). The participant will complete a HADS 10 evaluation form. Following the session the participant's GP will be sent a study notification letter.

The shorts have an order-to-delivery time of 2 weeks. Following delivery of these to the research site, the following activities will take place in sessions/intervals as follows

1. **Baseline session.** i. strength testing, questionnaires and interview completion. ii. shorts fitting and education, standardised method. Orthosis and exercise education will then be provided. The outcome measures gathered at baseline and followup will include: iHOT-12 questionnaire Orthotics Prosthetics Users Survey (OPUS) satisfaction subscales Hand Dynamometer - muscle strength by hip degree of movement.
Participants will be directed to wear the lycra shorts during all daily activity and physiotherapy exercise, where possible and diarise their experiences.
2. **Intervention window.** During the 12 weeks home trial period each participant will complete a formatted daily exercise and lycra garment intervention diary. Participants will be provided with a support contact telephone/email. All contact will be fully summarised in the participant activity timeline log.]
3. **Follow up session:** strength testing, follow up and repeat OPUS questionnaires and interview. Participant debrief either during this session or as a follow up communication.

4. At the **study conclusion** each participant will be asked to complete an interview and receive a debrief of their personal study data. They will be asked to reflect upon their qualitative experience and perceived personal and generalisable benefits of current and planned research into such conservative therapies.

Data will be collected using paper Case Report Forms (CRFs) designed by the research teams and stored in locked cabinets within the clinical facility.

The scores from the validated questionnaires, patient diaries and comments recorded at follow-up will be digitised and recorded on secure databases. As is appropriate in a small-scale study, quantitative results will be considered as descriptives such as mean, median, mode, percentage, frequency, skewness, and range. Qualitative data will be evaluated by analysing the content for systematic themes, patterns and features in participant experience.

All databases used during the study will be on password and firewall protected, NHS Trust proprietary systems and private cloud channels accessible only the research team.

Participant-specific study records will be anonymised by coding, with administrative decoding under the control of Principal Investigator (PI) only, in accordance with the NHS Code of Practice for Confidentiality.

Where hard copy records or questionnaires are generated during the study, these will be scanned electronically, and the hard copies will be destroyed. Research data will be stored on password protected Trust systems and accessible only by the research team.

Research data will be stored for 5 years following completion of the study. Personal data will be stored and accessed for the limited period of 12 months.

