3. THEORETICAL FRAMEWORK

The intervention, dynamic lycra shorts, are a made-to-order CE marked item which are marketed towards treating the symptoms of joint hypermobility amongst many other pathologies. No generalisable peer-reviewed evidence currently exists to support their treatment effectiveness in the current population of interest, as an adjunct to current approach which is based around exercise and education. Furthermore, qualitative aspects of use of these highly compressive lycra garments, such as impact on

self-care or comfort, that could negatively impact on sustained use have not been explored in the peer-reviewed literature. Before embarking upon a randomised trial it is important to confirm; the incidence of presentation of the target population, hypermobile DDH patients who are suitable for study inclusion.

- the fraction of whom are likely to consent and then choose to remain within the study protocol until the planned conclusion.
- extent of compliance with the intervention.
- identify aspects of the protocol that, through researcher and participant experience, may require modification.
- gain informed participant feedback as to the potential benefits of further research on this and similar topics.
- the incidence of anxiety and/or depression in the target population, which is thought to be common and could be an important variable in determining the outcome of treatment.

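### Three secondary outcomes do not match the session schedule: HADS has no follow-up, goal attainment is assigned to no named session, and garment satisfaction is asked before the garment is fitted

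*Protocol*

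**What the plan says.** **Outcome list (section 4).** The primary outcome is iHOT-12. There are six secondary outcomes: hip strength by dynamometer, GAS, HADS, OPUS HQOL, OPUS Lower Extremity Functional Status, and OPUS Satisfaction questions 1-9. Three of them carry a stated purpose that bears on timing:

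- "Hospital Anxiety & Depression Scale" is glossed as "Effect on mental health".
- GAS evaluates how far the patient's "individual goals are achieved over the course of study intervention".
- OPUS Satisfaction covers "fit and comfort of the Orthotic garment intervention".

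Section 3 gives HADS a second possible use. Before a randomised trial, the team wants to know "the incidence of anxiety and/or depression in the target population", as a variable that might influence the result of treatment.

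**Sessions (section 5).**

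- *Recruitment session:* consent, hypermobility status, measurement for the shorts, and HADS: "The participant will complete a HADS 10 evaluation form". Delivery of the shorts then takes 2 weeks.
- *Baseline session:* step i is strength testing, questionnaires and interview; step ii is fitting of the shorts and education. The list for this visit and the later one reads: "The outcome measures gathered at baseline and followup will include: iHOT-12 questionnaire Orthotics Prosthetics Users Survey (OPUS) satisfaction subscales", followed by the hand dynamometer.
- *Follow up session:* "strength testing, follow up and repeat OPUS questionnaires and interview".
- *Study conclusion:* an interview and a debrief.

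**The concern.** When an instrument is given is a protocol matter. An analysis plan written later cannot supply a follow-up HADS that nobody completed, or goals that nobody recorded before the shorts were worn.

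Section 5 describes the design as two repeated measurements. Sections 2 and 4.2 say the study should give early indications of effect, inform a power calculation and refine the measures for a later trial. A secondary outcome described as an effect, or as progress over the intervention, therefore needs a value on each side of the intervention. A question about a garment needs a garment that has been worn.

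If sites follow section 5 as written, no change in HADS can be described, and nothing ensures that goal attainment can be scored. Participants would also be asked at baseline about the fit and comfort of shorts they have not yet put on. With 8-12 participants (section 7.5), there is little room to make good a missed assessment.

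**Working it through.** No calculation applies. The check sets each outcome in section 4 against the sessions in section 5 that name it.

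| Outcome (section 4) | Recruitment | Baseline | Follow-up | Does the timing fit the stated purpose? |
|---|---|---|---|---|
| iHOT-12 (primary) | – | listed | listed | yes |
| Hip strength | – | listed, step i | listed | yes |
| HADS | named | not named | not named | no, for an effect; yes, for frequency |
| GAS | – | not named | not named | no named session |
| OPUS Satisfaction 1-9 | – | listed, before fitting | listed | follow-up only |
| OPUS HQOL | – | not named singly | covered by the general OPUS wording | ambiguous at baseline |
| OPUS Lower Extremity Function | – | not named singly | covered by the general OPUS wording | ambiguous at baseline |

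**HADS.** There is one named time point, before the shorts exist. Within-person change is the follow-up value minus the pre-garment value. The second term is scheduled and the first is not. A single value does meet the section 3 aim.

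**GAS.** The definition in section 4 compares achievement with individual goals over the intervention. That requires goals recorded at the start and a score at the end. Neither step appears by name in the recruitment, baseline, follow-up or conclusion sessions.

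**OPUS Satisfaction.** The questionnaires belong to step i of the baseline session and fitting to step ii. The baseline answer therefore has no object. The follow-up answer, after the 12-week home period, does.

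**OPUS HQOL and Lower Extremity Function.** The baseline and follow-up list names only the satisfaction subscales. The follow-up session, however, speaks of repeating OPUS questionnaires in the plural, which implies an earlier administration. The text points both ways.

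**Count for the six secondary outcomes:** 3 mismatched (HADS, GAS, Satisfaction) + 2 ambiguous (OPUS HQOL and function) + 1 clear (strength) = 6.

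**The case against.** The best defence is that the schedule is not written as exhaustive. The list is introduced as what the measures will include, and both the baseline and follow-up sessions refer to unspecified questionnaires. The baseline interview would be a natural place to set goals, and the definition of GAS already implies that they are set in advance. The study flow chart is not reproduced in the text available, and the case report forms are not part of the protocol text; either might place HADS or GAS. The study is descriptive, is chiefly about practicality, and counts refinement of its measures as an output.

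Much of this stands, and it rules out several stronger readings that a reader might infer:

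- *That the schedule fails to collect the secondary outcomes in general, or that only strength has usable data before and after.* The documents do not support this. The wording on repeated OPUS questionnaires leaves HQOL and function ambiguous, not omitted.
- *That the recruitment HADS is useless as a baseline.* It is taken before the garment is fitted and can stand as the pre-garment value. It also fully serves the section 3 aim.
- *That satisfaction data are lost, or that a meaningless change score is planned.* The follow-up score is collected, and section 5 plans descriptive summaries without announcing a change in satisfaction.
- *That goals will be set retrospectively.* Nothing says so; the gap is that no session is named.

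The defence does not remove the core. Section 5 names HADS at one particular session and names other instruments at the later ones, so a reader would take its absence at follow-up as intended. For satisfaction, general wording does not help, because the unsuitable time point is stated outright.

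**Conclusion.** The point holds for three of the six secondary outcomes. As named in the protocol, HADS has one time point and cannot describe an effect. GAS has no named session although its definition needs two. OPUS Satisfaction has a baseline score that cannot be interpreted beside a follow-up score that can. For OPUS HQOL and Lower Extremity Function, the finding is only that the baseline wording needs to be made clear.

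This is a should-fix point. The primary iHOT-12 and hip strength are in the baseline and follow-up list, and the study is a descriptive feasibility study of 8-12 people. It is still worth settling before enrolment, since a HADS value or a goal not recorded at the right visit cannot be recovered later.

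The conclusion rests on two assumptions: that staff follow the sessions as written in section 5, and that the flow chart and case report forms do not already place HADS and GAS at the visits where they are missing. If they do, section 5 needs only to be brought into line with them.

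**What to change.** In section 5, preferably as a short table of instruments by visit:

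1. **HADS:** add it at the follow-up session and keep the recruitment form as the pre-garment value. Alternatively, relabel HADS in section 4 as a baseline characteristic only, which matches section 3 and needs no extra form.
2. **GAS:** set and record goals before the shorts are fitted, and score them at follow-up.
3. **OPUS Satisfaction:** take it at follow-up only.
4. **OPUS HQOL and Lower Extremity Function:** name both at baseline and at follow-up.

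The cost is one extra HADS form (none if HADS is relabelled) and one GAS sheet per participant. For 8-12 participants that is at most 8-12 of each. Dropping the baseline satisfaction form saves 8-12 forms in return. No visit is added.

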8.6 Patient & Public Involvement

A stated purpose of this study is to garner participant experience and opinion as to the acceptability of the research, in individual terms of benefits *versus* any negative issues such as comfort or practicality in daily activities, as well as general benefits to patients.

Future study design will be informed by these findings. A summary of the study outcomes will be communicated to all study participants.

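### The end-of-study interview asks for the benefits of research but for no drawbacks, reasons for non-wear or view that further research is not worthwhile

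*Protocol*

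**What the plan says.** Protocol section 5, item 4 gives each participant an interview and a debrief at study conclusion. Its content is set out in one sentence with two parts:

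- An open part: "They will be asked to reflect upon their qualitative experience".
- A directional part, on "perceived personal and generalisable benefits of current and planned research into such conservative therapies".

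Other sections set wider aims. Section 3 says that aspects of use such as impact on "self-care or comfort, that could negatively impact on sustained use have not been explored in the peer-reviewed literature". Section 4.1 gives importance to "underlying, secondary or negative factors that may contribute to the net treatment effect". Section 8.6 describes acceptability as individual benefits weighed against "any negative issues such as comfort or practicality in daily activities". The Study Summary says that patients' opinions will help decide whether further quantitative study is justified.

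**The concern.** The protocol commits the study to weighing good against bad, but the one described interview names only the good side. The participant's opinion on further research feeds the study's main decision. A question that asks only what is beneficial about research gives no natural opening to say that it is not worth pursuing.

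The setting adds to this. Participants are unblinded (section 5). The investigator who triages referrals also delivers the participant-facing protocol (section 7.1) and takes consent (section 7.9). Participants may keep the shorts if these prove to help them personally (section 7.8). Each of these could nudge answers towards the favourable, and neutral wording is the simplest safeguard.

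**Working it through.** No arithmetic applies: the protocol gives no figure on this point. The check is a comparison of texts.

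1. **Which text fixes interview content?** Section 5 mentions an interview at baseline (item 1), at follow-up (item 3) and at study conclusion (item 4). Only item 4 says what is asked. Section 5.1 ends the study at the 12-week follow-up session, so items 3 and 4 may describe the same visit.

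2. **What does item 4 ask?** The open prompt on experience is neutral and can admit problems. The second prompt is about benefits, and they are the benefits of research, not of wearing the garment. No drawback is named for either.

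3. **Which aim does the second prompt serve?** It matches a bullet in section 3, to "gain informed participant feedback as to the potential benefits of further research on this and similar topics". That bullet also mentions benefits only. Section 8.6 covers similar ground, individual and general. At the individual level it sets benefits against negative issues; at the general level it too names benefits alone. Item 4 keeps the individual and general pair but drops the negative half.

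4. **Where else could negative experience be recorded?**
   - *Comfort:* section 4 lists "OPUS SATISFACTION (2014) Qs 1-9 fit and comfort of the Orthotic garment intervention", and section 5 repeats OPUS at follow-up. This is a direct structured prompt.
   - *General experience of wear:* the formatted daily diary over the home period (section 5, items 1 and 2). Its fields are not described.
   - *Other comments:* the follow-up interview, recorded follow-up comments and the log of participant contacts (section 5). No topics are stated for these.
   - *Risk:* section 8.1 deals only with safeguarding.

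5. **What is left uncovered?** Comfort is covered by OPUS. Self-care and practicality could surface in the diary or in the open prompt, but the protocol names neither as a topic to be asked about. No described instrument expressly asks when and why the shorts were not worn, although section 3 wants to know the extent of compliance. Nothing invites the view that further research is not worthwhile.

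**The case against.** The case against is substantial, and most of it stands.

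- **The benefits in question are those of research.** A reader might infer that participants are led to praise the shorts. The text does not say so. The prompt carries out a listed aim and does not directly steer answers about discomfort or non-wear. Any effect on reports of wear would be indirect; the direct effect is on the opinion about further study.
- **The same sentence opens neutrally.** A question about experience can draw out discomfort, self-care difficulty or no change. This stands.
- **Other sources exist.** The OPUS comfort items, the diary and the follow-up interview can all record problems. A reader might infer that barriers to wear will be under-reported, but with these routes in place that is not shown.
- **The interview is not ranked above the other sources.** Section 5 plans a content analysis of qualitative data without calling any source the main one. It would be wrong to treat this interview as the principal qualitative result.
- **One sentence is a summary, not a script.** A topic guide may exist and may be balanced. But the protocol refers to none, and what it does state is one-sided. That is different from leaving the detail unwritten.

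Matching the section 3 bullet explains the wording of item 4 but does not balance it, because the bullet has the same lean and section 8.6 promises more.

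**Conclusion.** The point holds in a limited form. Item 4 pairs a neutral prompt on experience with a prompt on the benefits of research alone. It names none of the negative issues that sections 3, 4.1 and 8.6 say the study should examine. The opinion on further study, which the Study Summary uses to judge its justification, is therefore invited from one side and may lean favourable. Reasons for not wearing the shorts are not expressly asked for in any described instrument.

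The size of the lean cannot be estimated. The documents give no rate at which problems occur or go unmentioned, and a calculation on assumed rates that treated the interview as the only source would ignore OPUS and the diary. The conclusion rests on the protocol's description of the interview, since no topic guide is shown. It affects no figure in the protocol, and is a minor improvement that costs little.

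**What to change.** Replace the second half of item 4 in section 5 with neutral wording, for example: *Each participant will be asked what became better, worse or stayed the same; about comfort, self-care and practicality; when and why the shorts were not worn; and whether further research is or is not worthwhile, and why.*

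If a topic guide already covers these subjects, item 4 need only refer to it and list them. The order of the questions and the way themes are reported can be left to the investigators.

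The cost is a change of wording and a few more minutes at a visit already planned, with no new instrument, staff or visit.
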